### **Secondary outcomes**

Secondary outcomes will compare participants' understanding of uncertainties, perceptions, and emotions after learning about a source of uncertainty relative to the difference in the control group. We will also assess trust associated with communicating uncertainty.

For understanding (measured on a 4-point Likert scale: strongly disagree to strongly agree), we will compare the percentage of participants who improved their understanding of the drug after being randomized to a source of uncertainty. For perceptions (measured on a 4-point Likert scale: very uncertain to very certain), we will compare the percentage of participants who were less certain that the drug would work well after learning about a source of uncertainty, and for emotions (measured on a 4-point Likert scale: extremely worried to not worried at all), we will compare the percentage of participants that were more worried about taking the drug after learning about a source of uncertainty. To assess trust, we will ask participants about their perceived trust in the information and the source of the information (measured on a 4-point Likert scale: not at all trustworthy to very trustworthy), and whether learning about uncertainties made them more or less trusting in the FDA (measured on a 4-point Likert scale: less trusting to more trusting).

### **Statistical analysis**

For the primary analysis comparing differences between the experimental conditions and the control group, we will use generalized estimating equations. To compare differences between groups in trust, which was only measured post-intervention, we will use  $\chi^2$  tests. As a sensitivity analysis we will use the  $\chi^2$  test (or Fischer's exact test as appropriate) to evaluate the percentage difference between groups in participants who were likely to take the drug post-intervention. To provide comparable estimates of the within group differences (changes from pre to post responses) for the trial, we will use McNemar's  $\chi^2$  test for paired data.

We powered the trial to detect a between group difference of 10% (65% post intervention for control vs 55% post intervention for the experimental groups) based on findings from the first trial, with 90% power and a two-sided alpha of 0.05. We aimed to recruit 600 participants per group in case of dropouts or errors during survey completion.

We plan to exclude participants who complete the survey in less than 150 seconds, a conservative cutoff that is consistent with other studies. We will also exclude participants who do not complete the survey and who provide straight-line responses.

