## **Procedure**

At the start of the survey, participants will be given a vignette describing a 38-year-old woman that was recently diagnosed with non-small cell lung cancer. The woman's doctor tells her about a new drug that was approved by the FDA for her disease and that is covered by her insurance. Participants will then be presented with a table summarizing the main benefits and harms of the drug, which was developed using the FDA's Drug Trials Snapshot for adagrasib.

In the pre-intervention phase, we will ask participants about how likely they would be to take the drug if they were in Alex's position, how certain they are that the drug will work, and how worried they would feel about taking the drug. We will also assess their understanding of the drug's benefits and risks. Participants will then be randomized to 0, 1, 2, 3 or 4 statements about sources of uncertainty with the drug's evidence. The post-intervention questions will re-assess decision-making, perceptions, emotions, and understanding, as well ask participants about their trust in the information that they were given, and the FDA.

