## **Primary outcome**

The primary outcome is the pre-post change in participants decisions to take the new cancer drug in each experimental condition relative to the control group. Decision-making was

measured using a 4-point Likert scale: very likely, somewhat likely, somewhat unlikely, and very unlikely. For the primary analysis we will categorize participant responses as binary and focus on participants who changed their decisions from likely (pre-intervention) to unlikely to take the drug (post-intervention).

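### The primary GEE is not specified and, read as a difference of pre-post changes, gives up precision that adjusting for the pre-randomisation answer would recover; the loss depends on an unstated correlation

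*Combined protocol and SAP*

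**What the plan says.** The Primary outcome section of the combined protocol and SAP states: "The primary outcome is the pre-post change in participants decisions to take the new cancer drug in each experimental condition relative to the control group". The four-level answer is made binary, and the analysis is to "focus on participants who changed their decisions from likely (pre-intervention) to unlikely to take the drug (post-intervention". The first sentence describes a difference of changes between arms; the second could mean a single switch indicator per person.

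The Statistical analysis section gives the primary model in one sentence: "For the primary analysis comparing differences between the experimental conditions and the control group, we will use generalized estimating equations". It states no link, model terms, working correlation or covariates, and does not say whether the arms share a pre-intervention mean.

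The Procedure section puts the pre-intervention questions first: "Participants will then be randomized to 0, 1, 2, 3 or 4 statements about sources of uncertainty with the drug's evidence". So Q4 (decision), Q5 (certainty) and Q6 (worry), in Survey Sections B to D, all precede randomisation.

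The sensitivity analysis is a chi-square test "to evaluate the percentage difference between groups in participants who were likely to take the drug post-intervention", which uses no baseline answer. Power was also set on post-intervention proportions: 65% versus 55%, 90% power, two-sided alpha 0.05, with 600 recruited per group.

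**The concern.** Because Q4 is answered before randomisation, the arms have the same expected baseline and any observed difference is chance. A group-by-time contrast with a free baseline in each arm subtracts that chance difference at full weight. Baseline adjustment subtracts only the part that predicts the post-intervention answer.

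Making the baseline binary discards more. A *somewhat likely* respondent should cross to unlikely more readily than a *very likely* one, yet the binary pre-answer treats them alike.

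At stake are wider confidence intervals for all four arm-versus-control contrasts than the collected data require, and a primary analysis whose precision was not what the sample-size calculation assumed.

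**Working it through.** **1. The plan's own figure.** For 65% versus 55%, the pooled normal formula at two-sided 0.05 and 90% power gives 503 per group. Recruiting 600 leaves (600 − 503)/600 = 16% for losses; the plan states no allowance. Power of the post-only comparison is 90.0% at 503 and 94% at 600. The target is sound for that comparison.

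**2. Chance imbalance.** The baseline rate is not in the documents; assume 65%. The SD of the baseline difference between two arms of 600 is √(2 × 0.65 × 0.35/600) = 0.0275, or 2.8 points (95% range ±5.4), against a 10-point target.

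**3. General result.** With equal variances, a change contrast has variance proportional to 2(1 − r) and an adjusted one to 1 − r². Their ratio is (1 + r)/2, so the loss is (1 − r)/2: 25% at r = 0.5, 15% at 0.7, 10% at 0.8.

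**4. With the planning rates, adjusting for the binary pre-answer.** Inputs: V_pre = V_control = 0.65 × 0.35 = 0.2275; V_exp = 0.55 × 0.45 = 0.2475; covariance in each arm = r√(V_pre × V_post), so the covariances sum to C = r(0.2275 + 0.2373) = 0.4648r.
- Change contrast: n × variance = 0.2275 + 0.2475 + 2 × 0.2275 − 2C = 0.930 − 0.9296r.
- Adjusted contrast: n × variance = 0.475 − C²/(2 × 0.2275).
- Power = Φ(0.10/SE − 1.96).

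| r | change | adjusted | loss | power at 600, change / adjusted | power at 500, change / adjusted |
|---|---|---|---|---|---|
| 0.33 | 0.623 | 0.423 | 32% | 87% / 96% | 81% / 93% |
| 0.40 | 0.558 | 0.399 | 28.5% | 91% / 97% | 85% / 94% |
| 0.50 | 0.465 | 0.356 | 23% | 95% / 98% | 91% / 96% |
| 0.60 | 0.372 | 0.304 | 18% | 98% / 99% | 96% / 98% |
| 0.70 | 0.279 | 0.242 | 13% | 99.6% / 99.9% | 98.8% / 99.5% |
| 0.80 | 0.186 | 0.171 | 8% | over 99% / over 99% | over 99% / over 99% |

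The change contrast matches the post-only comparison when 0.930 − 0.9296r = 0.475, that is r = 0.49, and is better above that. With these rates r cannot exceed √[(0.55 × 0.35)/(0.65 × 0.45)] = 0.81 in an experimental arm. In simulation (4,000 runs per scenario) both estimators averaged about −10 points, so there is no bias. A logit-scale group-by-time GEE had power one to two points below the risk-difference version in the scenarios with r up to 0.5.

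**5. Adjusting for four-level Q4.** Assumptions: latent-normal items, 70% likely before (split 30/40/18/12% from very likely to very unlikely), 65% versus 55% after. The adjusted variance is the sum over arms of Var(Y − m(X)), where m(X) is the expected post-answer given the pre-category.

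| r (binary) | variance cut, binary pre-answer | four-level Q4 | four-level Q4 plus one further pre-item |
|---|---|---|---|
| 0.40 | 26% | 31% | 34% |
| 0.48 | 22% | 29% | 31% |
| 0.58 | 17% | 27% | 28% |
| 0.70 | 12% | 23% | 24% |
| 0.78 | 8% | 21% | 21% |

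Allowing a 65% baseline and arm-specific r, the four-level range is about 20–33%. At the very top of the r range it can fall slightly under 20%, depending on the category split. Most of the gain comes from Q4; a further item adds 0 to 3 points.

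**6. Switch indicator.** If the outcome is one likely-to-unlikely indicator per person, there is no baseline to subtract, but four-level Q4 still predicts switching. Adjustment cuts variance by about 15–21% under the same assumptions.

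**The case against.** The strongest reply is that this criticises one assumed form of an unspecified model. A reader might infer that the plan uses the pre-answers only as a first time point with a free baseline per arm. It does not say so: a GEE with a common baseline, or a one-row switch indicator, also fits the text. That stands, and the point is therefore conditional on the most natural reading.

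A reader might also take a loss of a quarter to a third as established. It is not. The same question is repeated within one survey, and controls see no uncertainty statement, so a high r is plausible, especially in the control arm. With r of 0.9 in control and 0.7 in an experimental arm, the loss relative to binary adjustment is only 8%. The four-level figures hold up better at high r, but rest on the latent-normal assumption.

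Third, a reader might infer that the trial is biased or underpowered. Neither follows. Carrying chance imbalance and losing precision are one effect, and the stated 90% power is met at 600 analysable per arm for r of about 0.4 or more. However, 600 is a recruitment target, and exclusions for speed, incompleteness and straight-lining will reduce it by an unknown amount.

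**Conclusion.** The point holds as a matter of precision and specification, not validity. The documents establish that the primary contrast is a change relative to control, that the GEE is otherwise undefined, that no baseline adjustment is mentioned, and that suitable covariates are collected before randomisation. A free-baseline group-by-time contrast is then inferior to an adjusted one for every r below 1.

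The ranges in the working rest on assumed baseline rates of 65% or 70%, the planning rates of 65% versus 55%, latent-normal items for the four-level results, and r between about 0.4 and 0.8. None of these except the planning rates comes from the documents. Power for 10 points is in doubt only where r is low: under about 0.4 with 600 analysable per arm, or under about 0.5 with 500. The amendment is worth making because precision also matters for the smaller differences that may separate one, two, three and four statements.

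**What to change.** In the Statistical analysis section, write out the primary model: post-intervention binary decision on arm, adjusted for pre-intervention Q4 as four categories, with robust standard errors. Report each arm-versus-control effect as a standardised risk difference in percentage points with a 95% confidence interval, which is the scale of the planning target. Q5 and Q6 may be added but bring little.

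If a two-time-point GEE is kept, state its link and terms, constrain the pre-intervention mean to be common to all arms, and use a non-independence working correlation. Under working independence the constraint returns essentially the post-only comparison. With the binary answer at both times, this version should recover about the binary-baseline gain, not the four-level gain.

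If the switch indicator is the intended outcome, say so. Then either use a linear-probability model adjusted for four-level Q4, or analyse respondents likely at baseline, adjusted for *very* versus *somewhat* likely. Those already unlikely cannot switch, so a logistic model on all four categories would separate.

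The cost is SAP wording only, with no new questions and no change in sample size. The choice should be fixed before outcomes are examined by arm.

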## **Section A: Sources of prescription drug information**

**First, we want to learn about how you find information about prescription drugs.**

1. When you are looking for information about prescription drugs, how often do you use each of the following sources? (Matrix grid response options: Never, rarely, sometimes, often)
  - Print media (for example, New York Times, Wall Street Journal)
  - Broadcast media (for example, CNN, Fox, NBC)
  - Social media (for example, Facebook, Twitter [X], Instagram)
  - Government website (for example, FDA, CDC)
  - Other health websites (for example, WebMD, Mayo Clinic)
  - Advertisements (TV, online, or print)
  - Family or friends
  - Physician, nurse, or other health professional
2. Do you trust that information about prescription drugs from these sources is correct? (matrix grid with sources from above)
  - Strongly disagree
  - Somewhat disagree
  - Somewhat agree
  - Strongly agree
3. Overall, how easy is it for you to find trustworthy information about prescription drugs?
  - Very difficult
  - Somewhat difficult
  - Somewhat easy
  - Very easy

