### **Section J: Trust**

12. To what extent do you think the information about Zenova is trustworthy?

1. Not at all trustworthy
2. Somewhat untrustworthy
3. Somewhat trustworthy
4. Very trustworthy

13. To what extent do you think the FDA, who approved Zenova and produced this information, is trustworthy?

1. Not at all trustworthy
2. Somewhat untrustworthy
3. Somewhat trustworthy
4. Very trustworthy

14. Did having additional information about Zenova make you more or less trusting of the FDA?

1. Less trusting
2. Somewhat less trusting
3. Somewhat more trusting
4. More trusting

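### The unadjusted χ² tests of trust are valid but leave unused a related trust rating collected before randomisation; the likely gain in precision is small to moderate and free

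*Combined protocol and SAP*

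**What the plan says.** The Statistical analysis section gives trust its own method: "To compare differences between groups in trust, which was only measured post-intervention, we will use" χ² tests. It names no covariate and no effect measure for trust.

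The other outcomes have a pre-intervention measure. The Procedure section says participants are asked beforehand how likely they would be to take the drug, "how certain they are that the drug will work, and how worried they would feel about taking the drug". It adds: "We will also assess their understanding of the drug's benefits and risks". Sections F to I of the survey return to these topics after the intervention. The trust items (questions 12 to 14, Section J) come only afterwards. Question 13 reads: "To what extent do you think the FDA, who approved Zenova and produced this information, is trustworthy"?

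Section A opens the survey, ahead of the vignette ("First, we want to learn about how you find information about prescription drugs"). Its question 2 asks, on a 4-point agreement scale, "Do you trust that information about prescription drugs from these sources is correct"? This is answered for each source in a grid, and one row is "Government website (for example, FDA, CDC"). Allocation comes later, after the pre-intervention questions: "Participants will then be randomized to 0, 1, 2, 3 or 4 statements about sources of uncertainty".

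Neither Secondary outcomes nor Statistical analysis gives question 2 a role.

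**The concern.** The trial is built on pre-post measurement, and trust is the one named outcome family without a matched baseline. The plan gives that as the reason for a test that uses post-intervention answers alone. However, a related rating is already held for everyone, taken before randomisation. If people who trusted government drug information at the outset also tend to rate the FDA as trustworthy at the end, an unadjusted comparison leaves that person-to-person variation in the error term.

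What is at stake is the precision of a secondary comparison for which the plan states no power. Its validity is not in question.

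**Working it through.** **The plan's own figure.** The only sample size statement concerns the decision outcome: 65% against 55%, 90% power, two-sided alpha 0.05, with 600 recruited per group. With the pooled formula,

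n = [1.96·√(2·0.60·0.40) + 1.2816·√(0.65·0.35 + 0.55·0.45)]² / 0.10² = 503 per group (523 with continuity correction).

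The plan gives no loss rate, so 600 cannot be reproduced exactly. It fits an allowance of 1 − 503/600 = 16.2%, or 1 − 523/600 = 12.8%. I use 600 per arm below. The proportional gains do not depend on that choice.

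**Is question 2 a legitimate covariate?** It sits in the first survey section, before the vignette, and the Procedure places randomisation after the pre-intervention questions. The assigned arm therefore cannot influence it.

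**Size of the gain.** For a linear (mean or risk) difference, adjusting for a baseline item correlated r with the outcome multiplies the variance by about 1 − r². The standard error is multiplied by √(1 − r²), and the equivalent unadjusted sample is 600/(1 − r²). The documents do not give r, so a range is shown.

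Trust has no planning rates either. The last two columns assume 65% against 57% for a trust item split in two, purely as illustration. The unadjusted standard error is √[(0.65·0.35 + 0.57·0.43)/600] = 0.0281, so the 95% half-width is 1.96 × 0.0281 = 5.50 points. Power is Φ(0.08/SE − 1.96).

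| r (assumed) | Variance factor | Equivalent n per arm | 95% half-width (points) | Power for 8 points |
|---|---|---|---|---|
| 0 | 1.00 | 600 | 5.50 | 81.3% |
| 0.1 | 0.99 | 606 | 5.47 | 81.7% |
| 0.2 | 0.96 | 625 | 5.39 | 82.9% |
| 0.3 | 0.91 | 659 | 5.25 | 84.8% |
| 0.5 | 0.75 | 800 | 4.76 | 90.8% |

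**Does the approximation hold for items of this kind?** A simulation used 600 per arm, a 4-category baseline and a binary outcome. A linear model with the baseline as categories and robust standard errors was compared with the unadjusted difference.

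| Observed r | 1 − r² | Simulated variance ratio |
|---|---|---|
| 0 | 1.00 | 1.00 |
| 0.15 | 0.98 | 0.99 |
| 0.30 | 0.91 | 0.91 |
| 0.45 | 0.80 | 0.80 |

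Under no difference between arms, the adjusted test rejected in 4.3% to 5.4% of runs. Adjustment cost essentially nothing when the baseline was uninformative.

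**The case against.** The strongest reply is that nothing here is an error. Randomised arms may be compared on a post-only outcome with a χ² test, and chance imbalance in prior trust is already covered by that test's error rate. The plan describes no covariate adjustment for any outcome, so choosing one item for one secondary outcome is an optional refinement. This stands, and it sets the priority. It does not remove the gain.

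The reply also holds that question 2 is a loose proxy. It asks whether information from a source is correct, with FDA and CDC taken together under government websites. Question 13 asks about the FDA as approver and producer of the Zenova information, and question 12 about that information itself. This stands too. The correlation may be low, particularly for question 12, and at r of 0.2 or below the gain is negligible.

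A reader might go further in three ways that the documents do not support:

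- **That the planned trust comparison is biased or invalid.** Randomisation protects it.
- **That prior trust is a strong predictor, so the saving must be large.** No section reports a correlation. A figure such as 938 per arm requires r = 0.6 (600/0.64).
- **That question 2 is a true trust baseline and would allow a pre-post trust analysis.** Its wording and object differ from those of questions 12 and 13, so change scores would have no clear meaning.

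One might also fear that a null trust result will be taken as reassurance. The plan states no margin or hypothesis for trust, and a modestly narrower interval would not settle how a null result is read.

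**Conclusion.** The point holds as a free improvement to a valid analysis. The plan sets aside a pre-randomisation rating that bears on trust in the FDA, and so may give up some precision. The loss ranges from trivial (1% to 4% of variance at r of 0.1 to 0.2) through modest (9% at 0.3) to worthwhile (25% at 0.5). Where it falls depends wholly on a correlation that is assumed here. The gain should be larger for question 13 than for question 12.

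It also depends on the effect measure. The 1 − r² result applies to a mean or risk difference. Adjusting an odds ratio changes what is estimated and need not narrow its interval.

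Priority is minor, since trust is a secondary outcome.

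**What to change.** In Statistical analysis, add a pre-specified model for question 13, and likewise for question 12. Regress the response on arm, adjusting for the question 2 government-website rating, and report each experimental arm's adjusted difference from control with a 95% confidence interval. State the effect measure: a mean difference if the model is linear on the 4-point score, or a standardised risk difference if it is logistic or ordinal. Keep the χ² test as supportive. Leave question 14 as planned, because it already asks participants to report a change in trust.

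The cost is a sentence or two of analysis text. No survey item, participant or recruitment is added. Naming the covariate before the outcome data are examined also removes any later choice about which Section A item to use.

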### **Section F: Decision making**

8. Considering this additional information, if you were Alex and diagnosed with non-small cell lung cancer, how likely are you now to take Zenova?
  1. Very unlikely
  2. Somewhat unlikely
  3. Somewhat likely
  4. Very likely

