### **Section I: Understanding**

11. Please rate your agreement with the following statements again. (4-point scale)
  - Zenova's longer-term benefits and harms are well known
  - Zenova has been studied in patients that are similar to Alex (race and ethnicity)
  - Zenova improves how patients feel or how long they live
  - Zenova has a noticeable improvement for patients with non-small cell lung cancer

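### The completion rule drops randomised participants whose primary outcome is already recorded, and no planned analysis puts them back (minor)

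*Combined protocol and SAP*

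**What the plan says.** All references are to the combined protocol and SAP.

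- **Procedure.** The pre-intervention questions come first; then "Participants will then be randomized to 0, 1, 2, 3 or 4 statements about sources of uncertainty".
- **Primary outcome.** The four-point decision item is made binary, and the analysis will "focus on participants who changed their decisions from likely (pre-intervention) to unlikely to take the drug (post-intervention". Only question 4 (before) and question 8 (after) enter it.
- **Survey, Section F.** Question 8 directly follows the intervention page: "Considering this additional information, if you were Alex and diagnosed with non-small cell lung cancer, how likely are you now to take Zenova". Questions 9 to 29 come later and end with demographics.
- **Statistical analysis, exclusions.** "We plan to exclude participants who complete the survey in less than 150 seconds", and "We will also exclude participants who do not complete the survey and who provide straight-line responses". Neither completion nor straight-lining is defined.
- **Statistical analysis, sensitivity.** The only sensitivity analysis is a χ² or Fisher's exact test of the share likely to take the drug after the intervention. No all-randomised set is named, there or elsewhere.

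**The concern.** On its natural reading, the completion rule removes people who were randomised, saw their arm's material and gave both answers that the primary outcome needs. Leaving at the income question is enough. The planned analysis names no covariate that would need the later answers.

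This is exclusion on behaviour after randomisation. If leaving is related to switching and its frequency differs by arm, or if that relation itself differs by arm, the groups compared are no longer those that randomisation formed. Every planned analysis appears to rest on the same reduced set, so the results would not show whether this had happened.

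**Working it through.** **1. When the outcome is known.** Counting each grid row as one response:
- Before randomisation: question 1 (8) + question 2 (8) + questions 3–6 (4) + question 7 (5) = 25.
- Question 8 is response 26.
- After it: questions 9–10 (2) + question 11 (4) + questions 12–14 (3) + questions 15–20 (6) + questions 21–29 (9) = 24.

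The primary outcome is complete after 26 of 50 responses. The rule asks for the other 24.

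**2. The plan's own figure.** For 65% versus 55%, 90% power and two-sided alpha 0.05, the pooled two-proportion formula gives 503 per group. The target of 600 thus leaves room for 1 − 503/600 = 16.2% loss. No loss rate is stated, so 600 cannot be reproduced exactly. Power at 600 is 94.3%. The margin protects power; it does nothing for comparability.

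**3. Bias on the primary outcome.** The documents give no rates for loss or switching, so all rates here are assumed. Let s be an arm's true switch rate, d the share lost after question 8 and q the switch rate among those lost. Then

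retained rate = (s − d·q)/(1 − d).

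Take no true effect, s = 10% in both arms, and d = 10% (control) versus 15% (intervention), so 540 versus 510 remain. Type I error is from a two-proportion z-test, as a stand-in for the planned generalized estimating equations.

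| q | Control | Intervention | Bias (points) | Type I error |
|---|---|---|---|---|
| 0% | 11.11% | 11.76% | +0.65 | 6.3% |
| 5% | 10.56% | 10.88% | +0.33 | 5.3% |
| 10% | 10.00% | 10.00% | 0 | 5.0% |
| 15% | 9.44% | 9.12% | −0.33 | 5.4% |
| 20% | 8.89% | 8.24% | −0.65 | 6.6% |

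Cross-check: with the same s and q in both arms, bias = (s − q) × [0.15/0.85 − 0.10/0.90] = (s − q) × 0.0654. A 10-point gap between s and q gives 0.65 points.

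With 2% versus 5% loss, the bias is at most 0.32 points and type I error at most 5.4%.

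**4. Equal loss is not proof of no bias.** Suppose true switching is 10% versus 20%, both arms lose 5%, and quitters switch at 10% in control but 40% in the intervention arm. Control stays at 10.00%. The intervention arm becomes (0.20 − 0.05 × 0.40)/0.95 = 18.95%. The estimate is 8.95 points instead of 10. This needs intervention quitters to switch at twice their arm's rate.

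**The case against.** **Size.** Questions 9 to 29 are the same in every arm, so the documents give no reason to expect large differential loss after question 8. Bias vanishes if quitters switch at their arm's rate. Quitters who merely hold a different but stable view at both questions do not bias a null pre-post contrast. This stands, and it keeps the point minor.

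**Meaning of completion.** If the sponsor meant only that questions 4 and 8 are answered, the main point falls away. The text does not say so, and completing a survey ordinarily means all of it. One sentence would settle this.

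**Straight-lining.** A reader might infer that this rule will remove the people who understood the intervention. The four items of question 11 match the four statements in Table 1, so disagreeing with all four is the informed answer in the 4-statement arm. Such people would also count towards the understanding outcome, where "we will compare the percentage of participants who improved their understanding of the drug after being randomized to a source of uncertainty". But the plan does not say that question 11 would be used. A rule that needs one answer position throughout the survey would not flag them. What is supported is that the rule is undefined and a precaution is cheap.

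**Practical value of the exclusions.** Non-finishers may lack secondary outcomes and demographics, and some are inattentive. That is a real cost, but no reason to discard a recorded primary outcome.

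**Conclusion.** The point holds as a minor one. Following the stated rule discards randomised participants with a measured primary outcome, and no planned analysis would reveal the effect. Confidence is high on the text and low on size. In the null scenarios tried, bias is 0 to 0.65 points and type I error 5.0% to 6.6%, on assumed rates only; the direction cannot be known in advance.

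Three stronger readings are not supported:

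- *The primary result would be seriously biased.* Nothing in the documents shows that loss differs by arm or is related to switching.
- *Larger biases apply.* On the share likely to take the drug after the intervention (65% in both arms), 10% versus 15% loss with 45% of quitters likely gives 67.22% versus 68.53%. That is 1.31 points, with type I error 7.4%. It concerns the sensitivity endpoint, not the pre-post primary outcome.
- *The 150-second rule is itself a serious flaw.* Total time includes reading zero to four statements, so the rule is not wholly independent of arm. The documents give no timing data that would show a material effect, and dropping the rule has its own cost.

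**What to change.** 1. Analyse the primary outcome in all randomised participants with questions 4 and 8 recorded, in their assigned arm, whether or not they finished. The 150-second rule may stay for finishers.
2. Add one sensitivity analysis of all randomised participants with questions 4 and 8, without the speed and straight-line exclusions.
3. Define straight-lining in advance, on the pre-randomisation grids (questions 1, 2 and 7) and not on question 11.
4. Report exclusions by arm, reason and stage: before randomisation, from randomisation to question 8, and after question 8.

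**Cost.** Items 1 and 2 use data already collected and need only SAP wording. Denominators will differ between primary and secondary outcomes, and demographics will be incomplete for non-finishers. Some inattentive non-finishers stay in and slightly dilute the effect.

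An upper guide to that dilution uses the plan's power endpoint (65% versus 55% after the intervention, not switching). If a share l of 600 per group is wholly unresponsive to the statements, the contrast becomes 65% versus 65% − 10% × (1 − l):

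| Unresponsive share | Power if kept (600) | Power if excluded |
|---|---|---|
| 5% | 92.1% | 93.2% (570) |
| 10% | 89.1% | 92.0% (540) |
| 15% | 85.5% | 90.4% (510) |

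For non-finishers alone the share should be small. For speeders and straight-liners the trade-off is real, so item 2 is proposed only as a sensitivity analysis.
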